principal investigator. Pain scores during hospitalization and for the subsequent 1 week will be recorded and used for secondary analysis of daily pain scores during crisis.

Patients who during the course of the study have laboratory findings which reveal creatinine ≥ 1.5 mg/dL AND weight ≤ 60 kg; platelets $< 100 \times 10^9/L$; or develop AST or ALT > 3 times normal, will have study drug stopped and will be terminated from the study.

Patients on hydroxyurea will be included in the study and sub-analysis will be performed to control for potential differences. All patients despite treatment with hydroxyurea will need to meet inclusion criteria of having clinically significant pain which requires > 2 acute care visits.

4.2 Data and Statistical Analysis Aim 1

We power the study to test whether there is a significantly larger reduction in pain after administration of a daily prophylactic anticoagulation dose as compared to administration of a placebo. A total of 60 patients will be randomly assigned to each drug arm. The primary endpoint is the mean pain score per patient over each of four time periods. The design has two sources of variation: the variation between the patients receiving the same drug and the variation due to the interaction of time by the patients within drug arm. It is of interest to test whether the change in the pain score over the four time periods differs between the prophylactic anticoagulation dose arm and the placebo arm. From the literature the standard deviation of the mean pain score per patient is 1.5. Assume the true mean pain scores over the four time periods for the placebo and prophylactic anticoagulation dose arms are 3.9, 3.9, 3.9, 3.9 and 3.9, 3.12, 3.12, 3.12, respectively. Then, a total of 60 patients randomized equally to each drug arm will detect the difference in the change between the two arms in the mean pain scores over time, as specified by the preceding mean pain scores, with a power of at least 0.836 for a one-sided 0.05 test. Anticipating that 20% (10 patients) may have incomplete data (less than 75% of daily pain scores recorded or missing more than one dose of study drug per week), may be lost to follow up, or may drop out; we have also found a power of at least 78.4% for 50 patients.

We expect two positive effects from prophylactic doses of apixaban on the patient reported outcomes:

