- PROs assessing fatigue, physical function, and pain impact will improve in patients administered daily prophylactic dose apixaban compared to placebo.*
- We believe that there will be a significant correlation between PROs and pain scores.*

Statistical Analysis

The primary outcome of interest is to test the effect on the mean daily pain score due to the arm by time interaction. Secondary outcome will include comparison of daily pain scores while hospitalized between treatment arms and the number of hospitalizations during each treatment period.

Impact of Daily Prophylaxis Dose Anticoagulation with a Factor Xa Inhibitor (Apixaban) in Patients with Sickle Cell Disease

[figure not shown]
All analyses will be performed using SAS version 9 or greater (SAS Institute Inc., Cary, NC). Data will be analyzed using descriptive statistics including mean and standard deviation. Comparisons are to be performed using SAS's PROC GLM with a model that accounts for all fixed and random effects in the design.

5.0 Specific Aim 2: Determine the effect of prophylactic dose anticoagulation on markers of thrombin generation during outpatient steady state as well as inpatient VOC.

As described in section 3.0, we will perform a double blind, parallel group, placebo controlled feasibility study with an enrollment target of 60 patients (30 per arm).

5.1 Study Procedures Aim 2

As described earlier (Figure 1), patients begin a 1 month observation following randomization. Patients will have blood drawn on enrollment and when they return in 1 month (+/- 5 days) to begin study drug. Subsequent blood draws performed at 2 month intervals while on study drug. Blood draws will occur between 2 and 4 hours from previous dose taken and ± 5 days regardless of hospitalization. Patients will be called monthly between in person visits to assess for AE/SAE and to reinforce the importance of medication compliance. Graded incentives may be given monthly to encourage patients to continue on study and return for follow up blood draws.

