Primary analysis of daily pain scores will be performed for patients on treatment with Apixaban and compared to patients on placebo, to determine if treatment decreases daily pain scores. In addition, we will compare changes in thrombin generation from enrollment to 2 months for patients treated with Apixaban versus placebo.

Secondary analysis will be performed to evaluate differences when patients are hospitalized and on study drug versus placebo, as well as healthcare utilization for patients treated with Apixaban.

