9.1.2 Serious Adverse Events

A *serious AE (SAE)* is any untoward medical occurrence that at any dose:

- results in death
- is life-threatening (defined as an event in which the subject was at risk of death at the time of the event; it does not refer to an event which hypothetically might have caused death if it were more severe)
- requires inpatient hospitalization or causes prolongation of existing hospitalization (see **NOTE** below)
- results in persistent or significant disability/incapacity
- is a congenital anomaly/birth defect
- is an important medical event (defined as a medical event(s) that may not be immediately life-threatening or result in death or hospitalization but, based upon appropriate medical and scientific judgment, may jeopardize the subject or may require intervention [e.g., medical, surgical] to prevent one of the other serious outcomes listed in the definition above.) Examples of such events include, but are not limited to, intensive treatment in an emergency room or at home for allergic bronchospasm; blood dyscrasias or convulsions that do not result in hospitalization.)
- Suspected transmission of an infectious agent (e.g., any organism, virus or infectious particle, pathogenic or non-pathogenic) via the study drug is an SAE.

Although pregnancy, overdose, cancer are not always serious by regulatory definition, these events must be handled as SAEs. (See Section 9.3.6 for reporting pregnancies.)

NOTE: The following hospitalizations are not considered SAEs in BMS clinical studies:

- a visit to the emergency room or other hospital department lasting less than 24 hours that does not result in admission (unless considered an “important medical event” or a life-threatening event)
- elective surgery planned before signing consent
- admissions as per protocol for a planned medical/surgical procedure
- routine health assessment requiring admission for baseline/trending of health status (e.g., routine colonoscopy)
- medical/surgical admission for purpose other than remedying ill health state that was planned before study entry. Appropriate documentation is required in these cases.
- Admission encountered for another life circumstance that carries no bearing on health status and requires no medical/surgical intervention (e.g., lack of housing, economic inadequacy, caregiver respite, family circumstances, administrative).

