9.3.1 Serious Adverse Events

Following the subject’s written consent to participate in the study, all SAEs must be collected, including those thought to be associated with protocol-specified procedures. All SAEs must be collected that occur within 70 days of discontinuation of dosing of the investigational product. If applicable, SAEs must be collected that relate to any later protocol-specified procedure (e.g., a follow-up skin biopsy). The investigator should notify BMS of any SAE occurring after this time period that is believed to be related to the investigational product or protocol-specified procedure.

All SAEs whether related or unrelated to the study drug, apixaban, must be immediately reported to BMS (by the investigator or designee) within 24 hours of becoming aware of the event. If only limited information is initially available, follow-up reports are required. The original SAE form must be kept on file at the study site.

All SAEs should be faxed or emailed to BMS at:

Global Pharmacovigilance & Epidemiology
Bristol-Myers Squibb Company
[contact]
Email: [contact]

Impact of Daily Prophylaxis Dose Anticoagulation with a Factor Xa Inhibitor (Apixaban) in Patients with Sickle Cell Disease

Serious adverse events, whether related or unrelated to investigational product, must be recorded on the SAE page and reported expeditiously to BMS (or designee) to comply with regulatory requirements. An SAE report should be completed for any event where doubt exists regarding its status of seriousness.

All SAEs must be immediately reported by confirmed facsimile transmission (fax) and mailing of the completed SAE page. In some instances where a facsimile machine is not available, overnight express mail may be used. If only limited information is initially available, follow-up reports are required. (Note: Follow-up SAE reports should include the same investigator term(s) initially reported.) In selected circumstances, the protocol may specify conditions that require additional telephone reporting.

If the investigator believes that an SAE is not related to the investigational product, but is potentially related to the conditions of the study (such as withdrawal of previous therapy, or a complication of a study procedure), the relationship should be specified in the narrative section of the SAE page.

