9.3.3 Nonserious Adverse Events

The collection of nonserious AE information should begin at initiation of investigational product. Nonserious AE information should also be collected from the start of a placebo lead-in period or other observational period intended to establish a baseline status for the subjects.

If an ongoing nonserious AE worsens in its intensity, or if its relationship to the investigational product changes, a new nonserious AE entry for the event should be completed. Nonserious AEs should be followed to resolution or stabilization, or reported as SAEs if they become serious. Follow-up is also required for nonserious AEs that cause interruption or discontinuation of investigational product, or those that are present at the end of study participation. Subjects with nonserious AEs at study completion should receive post-treatment follow-up as appropriate.

All identified nonserious AEs must be recorded and described in the medical record.

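### A laboratory stop ends study participation as well as study drug, so daily pain scores after the stop have no stated route of collection

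*Combined protocol and SAP*

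**What the plan says.** Section 4.1 sets three laboratory limits that apply during the trial: creatinine of at least 1.5 mg/dL in a patient weighing 60 kg or less, platelets below 100 x 10^9/L, and AST or ALT above three times normal. A patient who reaches one "will have study drug stopped and will be terminated from the study". The sentence gives two separate orders, one about drug and one about participation.

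The primary endpoint in Section 4.2 is the mean pain score per patient in each of four time periods. The scores come from a daily log that patients bring to monthly visits (Section 4.1). A secondary outcome is "the number of hospitalizations during each treatment period".

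Some collection continues after drug is stopped:

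- **Serious events.** Section 9.1.2 counts as serious an event that "requires inpatient hospitalization or causes prolongation of existing hospitalization". Section 9.3.1 states: "All SAEs must be collected that occur within 70 days of discontinuation of dosing of the investigational product". After that, the investigator is asked to notify only SAEs believed related to the product or to a protocol procedure.
- **Nonserious events.** Section 9.3.3 states: "Follow-up is also required for nonserious AEs that cause interruption or discontinuation of investigational product".

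Section 5.2 describes the main comparison this way: "Primary analysis of daily pain scores will be performed for patients on treatment with Apixaban and compared to patients on placebo".

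**The concern.** Stopping a drug for safety does not require an end to observation. Here the two are joined. The trigger is a laboratory change after randomization that treatment could affect, so the patients who leave may differ between arms, and their unrecorded pain may differ from that of patients who stay. Missing scores of that kind can bias the comparison of arms.

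Section 4.2 allows for 20% (10 patients) with incomplete data, loss to follow-up or dropout, and quotes power for 50 patients. That allowance addresses precision. It does not correct a bias, and it does not recover scores that were never recorded. Without later scores, nobody can run an as-randomized analysis of these patients or check whether the loss mattered.

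**Working it through.** **Inputs.** Treatment lasts 6 months (Section 3.0), from Month 1 to Month 7 (Section 6), taken as 180 days with 30-day months. The SAE window is 70 days after the last dose (Section 9.3.1). There are 30 patients per arm (Section 3.0). The planned difference is 3.9 − 3.12 = 0.78 points (Section 4.2). The number of laboratory stops is not given.

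**1. The plan's power figure.** Section 4.2 states 0.836 for 60 patients and 0.784 for 50. I took the mean of the three later periods minus the first, with SD = 1.5 × √[(4/3)(1 − ρ)], where ρ is the within-patient correlation. At 30 per arm and one-sided 0.05, power is 0.540 at ρ = 0, 0.794 at ρ = 0.5 and 0.867 at ρ = 0.6. The stated 0.836 needs ρ of about 0.56, which then gives 0.773 at 25 per arm. The plan does not state ρ, so its figure can be neither confirmed nor refuted. This point does not depend on it.

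**2. Possible routes after a laboratory stop.**

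- *Pain log:* returned at study visits, which end with participation. Section 6 lists no early-termination visit and no off-drug schedule.
- *Follow-up visit:* tied to the End of Treatment visit (Section 3.0).
- *Telephone call two weeks after the last clinic visit (Section 6.1.4):* read generously, one more contact. It reviews how to complete the log and asks about adverse events, but collects no scores.
- *SAE reporting:* captures inpatient admissions for 70 days, then only events judged related.
- *Nonserious AE follow-up:* covers the event itself, not pain or admissions.

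**3. Days lost.** For a stop at Month m, treatment days left = 30 × (7 − m). Days beyond SAE cover = max(0, days left − 70).

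| Stop at | Pain-score days lost (of 180) | Share | Treatment days beyond SAE window |
|---|---|---|---|
| Month 2 | 150 | 83% | 80 |
| Month 3 | 120 | 67% | 50 |
| Month 4 | 90 | 50% | 20 |
| Month 5 | 60 | 33% | 0 |
| Month 6 | 30 | 17% | 0 |

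Pain scores are lost after any stop. Some treatment days lie beyond the SAE window only if 180 − s > 70, where s is the treatment day of the stop, that is, before day 110.

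**4. Effect on completeness.** Section 4.2 treats fewer than 75% of daily scores as incomplete. A stop at Month 5 leaves 120/180 = 67% of treatment days, or 150/210 = 71% with the observation month. Every stop at Month 5 or earlier therefore makes the patient incomplete through the protocol's own rule.

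**5. Scale only, on assumed values.** Suppose k = 1 to 3 of 30 patients stop in one arm with no offset in the other, and their later pain differs by d = 1 to 2 points. Shift in the arm mean = (k/30) × (months off drug/6) × d.

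- Low: (1/30) × (1/6) × 1 = 0.006 points, or 0.7% of 0.78.
- High: (3/30) × (5/6) × 2 = 0.167 points, or 21% of 0.78.

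The documents support neither k nor d. The formula also assumes that partial data enter in proportion to time. If incomplete patients are left out altogether, it does not apply.

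**The case against.** The case against runs as follows. This is a feasibility study. Screening excludes patients already at these limits, and perhaps nobody will reach one later. Section 5.2 can be read as an on-treatment comparison, and Section 4.2 counts more than one missed dose a week as incomplete, so off-drug scores might not enter the primary analysis anyway. The hospitalization outcome may mean time on drug, in which case later admissions fall outside it. Section 6 refers to Appendix A, which is not in the available text, and Section 9.3.6 mentions procedures for study discontinuation and follow-up. An early-termination contact may exist there.

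Most of this narrows the point. The number of stops is unknown, the hospitalization part depends on how the treatment period is read, and the finding is limited to the text available. The on-treatment wording does not remove the point. An as-randomized comparison can sit beside the planned one, but only if the scores exist, and daily scores cannot be recovered later.

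A reader might infer more than the documents support:

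- *All hospitalization data are lost after a stop.* They are not: admissions remain SAEs for 70 days, and related ones are notifiable afterwards.
- *The safety problem itself goes unfollowed.* Sections 9.3.1 and 9.3.3 already require follow-up to resolution or stabilization.
- *The Month 3 and Month 5 draws are when stops will occur.* Those draws list no creatinine, platelet or AST/ALT test, so a stop at any month needs a result from elsewhere.
- *Coagulation samples are lost.* Section 5.1 plans these: "Subsequent blood draws performed at 2 month intervals while on study drug". Their absence after a stop follows from the design.
- *The rule creates the gap for short visits.* Section 9.1.2 normally excludes from SAEs "a visit to the emergency room or other hospital department lasting less than 24 hours that does not result in admission", but Section 6 names no utilization form for any patient, so that gap is general.

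**Conclusion.** The point holds in limited form. As written, a laboratory limit ends observation as well as treatment, and later primary-endpoint scores have no route of collection in the available text. The loss is 150 to 30 of 180 treatment days for a stop at Month 2 to 6. Unrelated inpatient admissions in the planned treatment period are uncovered only for stops before about day 110, and only if that period means the planned 180 days.

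The documents do not show that the result will be biased, or in which direction. With no stops the bias is zero, and the 0.7% to 21% range is an illustration. The conclusion rests on 30-day months and on Appendix A containing no off-drug schedule. I would class the change as a cheap improvement.

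**What to change.** In Section 4.1, delete the clause that ends participation, so that reaching a limit stops study drug only. Add that, unless consent is withdrawn, the patient continues the existing pain log, telephone calls and clinic visits to Month 8, without the dose-timed research draws. The limits and the timing of stopping drug stay as they are.

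In the analysis text, add an as-randomized comparison that includes later pain and hospitalization data from these patients, reported beside the on-treatment analysis.

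**Cost.** One protocol sentence and one analysis sentence. For a stop at Month m, the patient keeps 8 − m clinic visits (6 to 2 for Months 2 to 6) and 9 − m calls (7 to 3), all already in the schedule. Off-drug data may dilute the as-randomized result slightly. If 1 to 3 of 30 patients stop and the effect is zero off drug, the 0.78-point difference falls by (1/30) × (1/6) × 0.78 = 0.004 to (3/30) × (5/6) × 0.78 = 0.065 points, or 0.6% to 8.3%. The on-treatment analysis is unaffected.

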3.0 Study Design

This is a double blind, parallel group, placebo controlled feasibility study (see figure 1) with an enrollment target of 60 patients (30 per arm). All subjects that meet inclusion criteria as an outpatient, following a 1 month observation, will be randomized to receive an oral prophylactic dose factor Xa inhibitor (Apixaban 2.5mg po bid) or placebo for 6 months. Subjects will return for a 30 day (+/- 5 days) follow-up visit after the End of Treatment (EOT) visit. Initial randomization will occur by computerized randomization technique by the investigational drug services (IDS) at Duke University Medical Center.

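### The planned hydroxyurea sub-analysis does not adjust the primary comparisons; baseline use should enter the primary models, for Aim 1 through a hydroxyurea-by-time term

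*Combined protocol and SAP*

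**What the plan says.** Section 4.1 (Study Procedures Aim 1) admits hydroxyurea users and says how they will be handled: "Patients on hydroxyurea will be included in the study and sub-analysis will be performed to control for potential differences". The next sentence holds users to the same acute-care-visit entry criterion as everyone else. The sub-analysis is not defined: no model, covariate, subgroup definition or interaction test is given.

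Section 3.0 (Study Design) describes allocation only as follows: "Initial randomization will occur by computerized randomization technique by the investigational drug services (IDS". No stratification factor is named. The target is stated there too: "with an enrollment target of 60 patients (30 per arm".

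In section 4.2 the primary Aim 1 test is the arm-by-time interaction on mean pain over four periods, fitted in SAS PROC GLM with the fixed and random effects of the design. Section 5.2 compares arms on change in thrombin-generation markers, sized on the change in D-dimer from enrolment to two months on drug. Hydroxyurea appears in neither. Section 6.1 collects medical history and concomitant medication at screening, so baseline use can be derived from data already planned.

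**The concern.** The stated purpose is to control for hydroxyurea, and the stated means is a sub-analysis. Separate estimates for users and non-users describe the effect in each group. They do not remove a chance imbalance in hydroxyurea use from the primary estimate, and they do not improve its precision. With no stratification and no model term, nothing in the plan serves the stated purpose for either primary comparison.

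At stake are a primary result that could be questioned if the arms differ by chance in a factor the plan itself flags, and small-subgroup results that might be read as more than descriptive. If the sub-analysis was meant as an adjusted supporting model, its form is open and could be chosen after the data are seen.

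**Working it through.** **Inputs from section 4.2.** Assumed period means for placebo and apixaban: "3.9, 3.9, 3.9, 3.9 and 3.9, 3.12, 3.12, 3.12, respectively", a difference of 0.78 in each of periods 2 to 4. Variation: "the standard deviation of the mean pain score per patient is 1.5". Result: "with a power of at least 0.836 for a one-sided 0.05 test". I take 60 patients in total, 30 per arm. One sentence ("A total of 60 patients will be randomly assigned to each drug arm") can be read as 60 per arm, but the rest of the text supports 60 in all. The hydroxyurea share and the within-patient correlation are not stated.

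**1. The plan's 0.836.** The stated inputs alone do not reproduce it.
- Simple two-mean comparison: 0.78 / (1.5 × √(4/60)) = 2.014; power Φ(2.014 − 1.645) = 0.644.
- Mean of periods 2–4 minus period 1, correlation ρ = 0: SD = 1.5 × √(4/3) = 1.732; power 0.540.
- Three-degree-of-freedom arm-by-time F test, ρ = 0: power 0.273.

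The contrast reaches 0.836 at ρ of about 0.56. This does not show that 0.836 is wrong, because the correlation it needs is not given. Below I take 0.836 at face value: noncentrality = 0.978 + 1.645 = 2.623.

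**2. What a hydroxyurea term does in the Aim 1 test.** Let patient *i* have on-treatment-minus-baseline contrast Dᵢ = mean(Y₂, Y₃, Y₄) − Y₁. A constant hydroxyurea effect γ enters all four Y values and cancels from Dᵢ. So a main effect alone should not move the arm-by-time test. In one simulated complete data set (60 patients, four periods, use 40% against 60% by arm):
- no hydroxyurea term: F = 1.283 on 3 and 174 df;
- hydroxyurea main effect: F = 1.283 on 3 and 174 df;
- hydroxyurea-by-time: F = 1.662 on 3 and 171 df.

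Only the time interaction adjusts the test. In Aim 2 the outcome is itself a change score, so a yes/no covariate on that change does the same job.

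**3. Chance imbalance, 30 per arm, assumed shares.** The SD of the between-arm difference in use at a 50% share is √(0.5 × 0.5 × 2/30) = 0.129, or 13 percentage points. The probability of a gap of at least 6 patients (20 points), from two independent binomials, is 0.155 at a 50% share, 0.12 at 30% and 0.07 at 20%.

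**4. Power within a subgroup holding share *s* of the patients:** Φ(2.623 × √s − 1.645).

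| Share | 20% | 30% | 40% | 50% | 60% | 70% |
|---|---|---|---|---|---|---|
| Power | 0.32 | 0.42 | 0.51 | 0.58 | 0.65 | 0.71 |

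An arm-by-hydroxyurea interaction as large as the whole treatment effect, at a half split, has power Φ(2.623/2 − 1.645) = 0.37, one-sided.

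**5. Cost of adjusting.** The loss of three degrees of freedom leaves power at 0.836 to three decimals. If hydroxyurea explains nothing and use is 60% against 40%, its correlation with arm is 0.2, and power is Φ(2.623 × √(1 − 0.04) − 1.645) = 0.82.

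**6. Possible gain.** If hydroxyurea explains a fraction R² of the contrast variance, power is Φ(2.623/√(1 − R²) − 1.645): 0.852 at R² = 0.05 and 0.869 at 0.10. To see what that requires, the contrast SD implied by 0.836 is 0.78 / (2.623 × √(4/60)) = 1.15. At a half split, users and non-users must differ in change by 2 × 1.15 × √R², about 0.51 to 0.73 points. A 20-point imbalance would then shift the treatment estimate by 0.2 times that, about 0.10 to 0.15 points.

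**The case against.** The strongest reply is that the primary test already protects itself. Each patient is their own control, a constant hydroxyurea effect cancels, randomisation balances use in expectation, and the common entry criterion on acute care visits may make users and non-users more alike in pain burden. The trial is called a feasibility study, and the sub-analysis is nowhere presented as powered or confirmatory. The term is undefined and could mean an adjusted supporting analysis. All of this stands. It narrows the issue to chance imbalance and precision for change over time, and to specification. It does not supply the control that section 4.1 promises.

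A reader might infer more, and the documents do not support it:
- *The primary result is biased.* Imbalance under randomisation is a matter of chance, and a constant effect on pain level drops out.
- *Each subgroup has 58% power.* That needs a half split, which the documents do not give, and it inherits the unreproduced 0.836.
- *Any baseline covariate would cure this at no cost.* A main effect alone changes nothing for Aim 1 in complete data, and adjustment can lower power slightly.
- *Adjustment will raise power.* The gains in step 6 need a hydroxyurea difference in change of about two-thirds to nine-tenths of the assumed apixaban effect (0.51/0.78 = 65%; 0.73/0.78 = 94%). Nothing in the documents supports that.
- *Hydroxyurea is an established prognostic factor here.* The plan speaks only of potential differences.

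**Conclusion.** The concern holds in a limited form. The stated means does not meet the stated purpose: estimates within users and non-users do not adjust either primary comparison, and neither the randomisation nor the primary models account for hydroxyurea. The consequence is unadjusted chance imbalance and possibly lost precision for change over time.

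The size is modest and depends on assumptions. A gap of 20 points or more has probability of about 0.07 to 0.155 for shares of 20% to 50%. Its effect on the estimate depends on how far hydroxyurea predicts change, which the documents do not state. The subgroup conclusion is firmer: across shares of 20% to 70%, with 0.836 at face value, power is about 0.32 to 0.71, below the plan's own figure throughout. The point about the main effect rests on algebra for complete data and needs no assumed share.

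**What to change.** Replace the sentence in section 4.1 and carry the change into sections 4.2 and 5.2, before unblinding:
- Define baseline hydroxyurea use (yes/no) from the screening medical history and concomitant medication.
- Aim 1: include hydroxyurea and hydroxyurea-by-time in the primary model or, equivalently, use hydroxyurea as a covariate on the on-treatment-minus-baseline contrast. State which form is used, because the present PROC GLM wording does not show whether a between-patient covariate would be crossed with time.
- Aim 2: include hydroxyurea as a covariate in the model for change in D-dimer.
- Report estimates within users and non-users as descriptive, with an arm-by-hydroxyurea interaction estimate and its confidence interval.

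The cost is wording, with no new data and no extra patients. The statistical price is up to three degrees of freedom and, in the unfavourable case of step 5, a little over one point of power (0.836 to about 0.82).
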